7.7.1 Dose Interruptions/Modifications for Specific, Non-liver Related, Toxicities

Recommendations for pazopanib (investigational product, IP) dose interruptions/modifications in case of specific treatment-emergent AEs are provided in Table 1.

Table 1 Dose Modification Algorithms for Potential Treatment-Related Adverse Events

AE Terms & Descriptions	Dose Modification Algorithms
-------------------------	------------------------------

AE Terms & Descriptions	Dose Modification Algorithms
Hypertension	
(A). Asymptomatic and persistent SBP of ≥ 140 and < 170 mmHg, or DBP ≥ 90 and < 110 mmHg, or a clinically significant increase in DBP of 20 mmHg (but still below 110 mmHg).	
Step 1. Continue investigational product (IP) at the current dose.
 
Step 2. Adjust current or initiate new antihypertensive medication(s).
 
Step 3. Titrate antihypertensive medication(s) during next 2 weeks as indicated to achieve well-controlled^a blood pressure (BP). If BP is not well-controlled within 2 weeks, consider referral to a specialist and go to scenario (B).

(B). Asymptomatic SBP ≥ 170 mmHg, or DBP ≥ 110 mmHg, or failure to achieve well-controlled BP within 2 weeks in scenario (A).	
Step 1. Consider reducing or interrupting IP, as clinically indicated.
 
Step 2. Adjust current or initiate new antihypertensive medication(s).
 
Step 3. Titrate antihypertensive medication(s) during next 2 weeks as indicated to achieve well-controlled BP.
 
Step 4. Once BP is well-controlled, restart IP dose-reduced by 200 mg if IP was interrupted.

(C). Symptomatic hypertension or recurring SBP ≥ 170 mmHg, or DBP ≥ 110 mmHg, despite modification of antihypertensive medication(s)	
Step 1. Interrupt IP
 
Step 2. Adjust current or initiate new antihypertensive medication(s).
 
Step 3. Titrate antihypertensive medication(s) during next 2 weeks as indicated to achieve well-controlled BP. Referral to a specialist for further evaluation and follow-up is also recommended.
 
Step 4. Once BP is well-controlled, restart IP dose-reduced by 200 mg.

(D). Refractory hypertension unresponsive to above interventions.	Discontinue IP and continue follow-up per protocol.
Prolongation of QTc Interval: If the QTc is prolonged, the ECG should be manually read to ensure accuracy of the reading. The values below refer to manually-read ECGs. Refer to Section 7.1.1 for ECG monitoring	
QTc $\geq 480 < 500$ msec	Continue IP; monitor as clinically indicated.
QTc ≥ 500 msec	Discontinue IP and continue follow-up per protocol.
Proteinuria	
UPC <3	Continue pazopanib at the current dose; monitor as clinically indicated
UPC ≥ 3 or 24-h urine protein ≥ 3 g	
Step 1. Interrupt IP.
 
Step 2. Weekly UPC or 24-hr urine protein monitoring until UPC is <3 or 24-hr urine protein is <3 grams. Then restart pazopanib dose-reduced by 200 mg.
 
Step 3. If UPC ≥ 3 or 24-h urine protein ≥ 3g recurs, repeat steps 1 and 2.
 
Step 4. If UPC ≥ 3 or 24-hr urine protein ≥ 3g recurs and the pazopanib dose can no longer be reduced, discontinue pazopanib and continue follow-up per protocol.

Hemorrhage /Bleeding: Investigate and document underlying etiology of the bleeding	
Grade 1	For hemoptysis, interrupt pazopanib and contact the Novartis Study Physician to discuss whether further treatment with pazopanib is appropriate.

	For other Grade I hemorrhage/bleeding events, continue pazopanib at the current dose; monitor as clinically indicated.
Grade 2	Step 1. If pulmonary or GI bleed (other than hemorrhoidal bleeding), discontinue IP and continue follow-up per protocol. Otherwise, interrupt IP until the AE resolved to \leq Grade 1. Step 2. Restart IP; consider reducing dose and monitor as clinically indicated.
Grade 3 or 4, or Recurrent \geq Grade 2 event after dose interruption/reduction.	Discontinue IP and continue with follow-up per protocol.
Venous Thrombosis (DVT, PE)	
Grade 2	Continue IP at the current dose; monitor as clinically indicated
Grade 3	Step 1. Interrupt IP. Step 2. Initiate and monitor anticoagulation as clinically indicated. Step 3. Resume IP at same dose only if all of the following criteria are met: 
 • The subject must have been treated with anticoagulant at the desired level of anticoagulation for at least one week. • No Grade 3 or 4 or clinically significant Grade 2, hemorrhagic events have occurred while on anticoagulation treatment. Subject should be monitored as clinically indicated during anticoagulation treatment and after resuming study treatment. When treating with warfarin, international normalized ratio (INR) should be monitored within three to five days after any change in IP dosing (eg, re-initiating, escalating/de-escalating, or discontinuing IP), and then at least weekly until the INR is stable. The dose of warfarin (or its derivatives) may need to be adjusted to maintain the desired level of anticoagulation
Grade 4 and/or PE	Discontinue IP and continue follow-up per protocol.
Arterial Thrombosis/Ischemia	
Any Grade	Discontinue IP and continue follow-up per protocol.
Thrombocytopenia: Investigate and document underlying cause	
Grade 1 or 2	Continue IP with current dose; monitor as clinically indicated.
Grade 3 or 4	Step 1. Interrupt IP until toxicity resolves to \leq Grade 2. Step 2. Restart IP dose-reduced by 200 mg and monitor as clinically indicated. If no recovery to \leq Grade 2 or recurrent Grade 3 or 4 thrombocytopenia, discontinue IP and follow-up per protocol.
Anemia: No specific dose reduction rules are indicated for anemia unless due to hemorrhage or bleeding as noted above.	
Palmar-plantar Erythrodysesthesia Syndrome	

Grade 1 Minimal skin changes or dermatitis without pain (erythema, oedema, hyperkeratosis)	1. Continue IP at present dose
Grade 2 Skin changes with pain; limiting instrumental activities of daily living (ADLs) (peeling, blisters, oedema, bleed, hyperkeratosis)	1. Hold IP 2. Treat as clinically appropriate 3. Upon resolution to Level 1 or better restart IP with a dose reduction to 400 mg 4. If recurrent consider a further dose reduction to 200mg or discontinuation
Grade 3 Severe skin changes with pain and limiting self care ADLs	1. Discontinue IP
Other Clinically Significant Adverse Events^b	
Grade 1	Continue IP; monitor as clinically indicated.
Grade 2 or 3, if clinically significant	Step 1. Interrupt IP until toxicity resolves to \leq Grade 1. Step 2. Restart IP dose-reduced by 200 mg and monitor as clinically indicated.
Grade 4	Discontinue IP and continue follow-up per protocol.

a. Well-controlled BP defined as SBP <140 mmHg and mean DBP <90 mmHg.
 b. AEs are graded according to NCI Common Terminology Criteria for Adverse Events v4.0 (NCI CTCAE v4)
 Abbreviations: BP, blood pressure; IP, investigational product.

7.7.2 Dose Interruptions/Modifications for Hepatotoxicity

AST, ALT and/or Bilirubin	
Isolated AST/ALT elevations between 3X ULN and 8X ULN	Reduce pazopanib dose to 200 mg QD, and monitor weekly until AST/ALT returns to ≤ 2.5 or baseline
AST/ALT >8 X ULN	Hold pazopanib until AST/ALT returns to ≤ 2.5 X ULN or baseline. If the potential benefit of reinitiating pazopanib treatment is considered to outweigh the risk for hepatotoxicity, then consider reintroducing pazopanib at a reduced dose of 400 mg once daily and measure serum liver tests weekly for 8 weeks only after discussion with the PI . If AST/ALT elevations >3 X ULN recur, then pazopanib should be permanently discontinued.
AST/ALT >3 X ULN and concurrent bilirubin elevations >2 X ULN	Permanently discontinue pazopanib.
Mild indirect hyperbilirubinemia, known or suspected Gilbert's syndrome, and elevation in AST/ALT >3 X ULN	Continue pazopanib, but monitor weekly until AST/ALT returns from >3 X ULN to grade 1 (NCI CTCAE) or baseline.

Severe hepatic impairment, defined as bilirubin >3 X ULN, regardless of any level ALT	Permanently discontinue pazopanib.
---	------------------------------------

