5.0 SUBJECT SELECTION

5.1 Inclusion Criteria

- 5.1.a Histologically or cytologically confirmed soft-tissue sarcoma, excluding alveolar and embryonal rhabdomyosarcoma, well- and dedifferentiated adipocytic sarcomas, Ewing's, osteosarcoma, or gastrointestinal stromal tumor. AJCC (6th Edition) Stage III or T2a Stage II or Stage IV-treatment naive patients planned for resection of the primary tumor, with resectable metastatic disease.
- 5.1.b Measurable disease greater than 5 centimeters in greatest dimension. Measurable lesions are defined as those that can be accurately measured in at least one dimension (longest diameter for non-nodal lesions and short axis for nodal lesions to be recorded) by chest x-ray, CT scan, MRI or with calipers by clinical exam. All tumor measurements must be recorded in millimeters (or decimal fractions of centimeters).
- 5.1.c Intermediate or high grade lesions: 2 or 3 on a scale of 1-3 or grades 2 to 4 on a scale of 1-4.
- 5.1.d Sarcoma located on upper (includes shoulder) or lower (includes hip) extremities or on the body wall.
- 5.1.e Life expectancy of greater than 6 months.
- 5.1.f ECOG performance status ≤ 1 (Karnofsky $\geq 80\%$; see **Appendix B**).

- 5.1.g No prior chemotherapy, radiotherapy, or antiangiogenic therapy.
- 5.1.h Age \geq 18 years
- 5.1.i No significant organ dysfunction with initial labs:

ANC	\geq 1500 / μ L
Hgb	\geq 9.0 g/dL
Platelets	\geq 100,000 / μ L
Creatinine	\leq 1.5 x ULN
Bilirubin	\leq 1.5 mg/dL
AST/ALT	\leq 1.5 x ULN

PT/INR/PTT within 1.2 X the upper limit of normal unless a subject is receiving Coumadin and has stable INR which is in range for the desired level of anticoagulation
- 5.1.j Normal cardiac function: LVEF \geq 50%
- 5.1.k Blood pressure (BP) no greater than 140 mmHg (systolic) and 90 mmHg (diastolic) for eligibility. Initiation or adjustment of BP medication is permitted prior to study entry provided that the average of three BP readings on baseline assessment prior to enrollment is less than 140/90 mmHg.
- 5.1.l Eligibility of subjects receiving any medications or substances known to affect or with the potential to affect the activity or pharmacokinetics of pazopanib will be determined following review of their cases by the Principal Investigator (see **Section 7.4** for further information).
- 5.1.m Women of child-bearing potential and men must agree to use adequate contraception.

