5.2. Exclusion Criteria

- 5.2.a Subjects with known brain metastases and/or unresectable sarcoma.
- 5.2.b Uncontrolled intercurrent illness including, active serious infection, symptomatic congestive heart failure, unstable angina pectoris, cardiac ventricular arrhythmia requiring anti-arrhythmic therapy, serious hepatic impairment, or psychiatric illness/social situations that would limit compliance with study.
- 5.2.c Pregnant or lactating women.
- 5.2.d Subjects with no additional active malignancy within the last 3 years.

- 5.2.e Subjects receiving other investigational agents.
- 5.2.f Subjects with a history of allergic reactions attributed to compounds of similar chemical or biologic composition to pazopanib or other agents used in the study.
- 5.2.g Subjects who have both bilirubin >ULN *and* AST/ALT >ULN
- 5.2.h Subjects with a urine protein/creatinine ratio greater than 1.
- 5.2.i Subjects with a baseline QTc of equal to or greater than 480 msec or other significant ECG abnormalities.
- 5.2.k Certain medications that act through the CYP450 system are specifically prohibited in subjects receiving pazopanib and others should be avoided or administered with extreme caution and require PI approval.
 - **Strong inhibitors of CYP3A4** such as ketoconazole, itraconazole, clarithromycin, atazanavir, indinavir, nefazodone, nelfinavir, ritonavir, saquinavir, telithromycin, voriconazole may increase pazopanib concentrations and are prohibited. Grapefruit juice is also an inhibitor of CYP450 and should not be taken with pazopanib.
 - **Strong inducers of CYP3A4**, such as rifampin, may decrease pazopanib concentrations, are prohibited. (See **Section 7.2**)
 - Medications which have narrow therapeutic windows and are substrates of CYP3A4, CYP2D6, or CYP2C8 should be avoided and, if necessary, administered with caution. (See **Section 7.2**)

A list of medications that are specifically prohibited or those that should be used with caution during this trial of pazopanib can be found in **Section 7.2**. Comprehensive lists of agents that could affect pazopanib through the cytochrome P450 system can be found in **Appendix D**.

Pazopanib, 800 mg once daily, has no effect on CYP2C9, CYP1A2, or CYP2C19 *in vivo* but does *in vitro*. Therefore, therapeutic doses of warfarin, a substrate of CYP2C9, and omeprazole, a substrate of CYP2C19 are permitted. Caffeine, a substrate of CYP1A2, is also permitted.

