G Pazopanib may be resumed 1 week after completion of post-operative therapy (chemotherapy +/- radiation) for those randomized to the treatment who had a response by imaging, to be continued for 1 year. Unblinding occurs during the first post-op visit after surgery.

H PEG-Filgrastim should be administered approximately 24-48 hours after completing chemotherapy. 10 days of filgrastim may be substituted.

I Mesna will be given at 400 mg/m². Post IFOS doses will be at 4 hours and 8 hours (+/- standard clinical dosing windows)

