Attribution: - The following are definitions for determining whether an adverse event is related to a medical product, treatment or procedure:

An adverse event is “**related or possibly related to the research procedures**” if in the opinion of the Principal Investigator, it was more likely than not caused by the research procedures.

Adverse events that are **solely** caused by an underlying disease, disorder or condition of the subject or by other circumstances unrelated to either the research or any underlying disease, disorder or condition of the subject are **not “related or possibly related.”**

If there is any question whether or not an adverse event is related or possibly related, the adverse event should be reported.

The Cancer Consortium Expedited Reporting Form should be completed for all adverse events that meet the expedited reporting requirements. The AE form should be faxed to the IRO at [contact]. All available information should be submitted.

It is the responsibility of the Principal Investigator and/or a designated staff member to notify Novartis, NIH, and the FDA of adverse events that meet expedited reporting (such as Serious Adverse Events) as required in the protocol.

Also considered serious for the purposes of this study:

- ALT $>3.0 \times$ ULN with concomitant elevation in bilirubin (defined as total bilirubin $<2.0 \times$ ULN or direct bilirubin 35%) or with hypersensitivity symptoms (e.g., fever, rash) – bilirubin fractionation should be performed in testing available.
- ALT $>8.0 \times$ ULN without bilirubin elevation (defined as total bilirubin $<2.0 \times$ ULN or direct bilirubin 35%) and without hypersensitivity symptoms (e.g., fever, rash) – bilirubin

fractionation should be performed if testing available.

Serious Adverse Events

For Open Label Portion of Study:

All SAEs arising during the study in subjects exposed to pazopanib will be reported to Novartis using copies of the original Case Report Form pages and within 24 hours of first becoming aware of the event, regardless of causality assessments.

For Blinded Portion of Study:

Study conduct procedures will be ensured and in place to allow for the expedited reporting of relevant SAEs to the appropriate regulatory authorities, IEC(s) or IRB(s) as required, during the course of the study.

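### The liver-toxicity table in Section 7.7.2 tells investigators both to hold and to continue pazopanib in a Gilbert's syndrome patient with AST/ALT above 8× ULN, and nothing says which row governs

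*Combined protocol and SAP*

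**What the plan says.** Section 7.7.2 sets pazopanib dosing by AST/ALT and bilirubin in a five-row table. Two rows matter here.

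- **Hold row (second).** The trigger is AST/ALT above 8× ULN. The action begins "Hold pazopanib until AST/ALT returns to" 2.5× ULN or baseline. Any restart is at 400 mg daily, needs prior discussion with the principal investigator, and carries weekly liver tests for 8 weeks.
- **Gilbert's row (fourth).** The trigger is mild indirect hyperbilirubinemia, "known or suspected Gilbert's syndrome, and elevation in AST/ALT >3 X ULN". The action is "Continue pazopanib, but monitor weekly until AST/ALT returns from >3 X ULN to grade 1 (NCI CTCAE) or baseline".

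The hold row makes no exception for Gilbert's syndrome. The Gilbert's row has no upper AST/ALT limit. By contrast, the first row (reduce the dose) is restricted to isolated elevations and stops at 8× ULN.

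**The concern.** A dose-modification table should give one action for each patient state. Here one identifiable state, Gilbert's syndrome with a mild bilirubin rise and AST/ALT above 8× ULN, attracts two opposite actions. An investigator who treats the more specific row as overriding the general one would keep dosing through a level of liver injury at which the plan otherwise stops the drug. An investigator who treats 8× ULN as a ceiling would hold. Section 4.1 describes a multi-center study, so the same patient could be handled differently at different sites. What is at stake is patient safety and consistent conduct, not an estimate or an error rate.

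**Working it through.** The plan states no figure to reproduce. The check compares the rows, looks for a tie-breaker, then asks when and how often the overlap could matter.

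**1. The five rows of Section 7.7.2**

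| Row | Trigger | Action |
|---|---|---|
| 1 | Isolated AST/ALT 3× to 8× ULN | Reduce dose, monitor weekly |
| 2 | AST/ALT >8× ULN | Hold |
| 3 | AST/ALT >3× ULN with bilirubin >2× ULN | Permanently discontinue |
| 4 | Mild indirect hyperbilirubinemia, Gilbert's, AST/ALT >3× ULN | Continue, monitor weekly |
| 5 | Bilirubin >3× ULN | Permanently discontinue |

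**2. Which rows apply to a Gilbert's patient**

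The protocol does not define mild, so bilirubin is assumed to be 1.4× ULN. That is below the triggers of rows 3 and 5. Isolated in row 1 is read as having no accompanying bilirubin rise.

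| AST/ALT (× ULN) | Rows met |
|---|---|
| 4 | 4 only |
| 8 | 4 only |
| 8.1 | 2 and 4 |
| 12 | 2 and 4 |
| 25 | 2 and 4 |

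The overlap is therefore the whole range above 8× ULN, and there the drug would have to be both held and continued.

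**3. Is there a tie-breaker elsewhere?**

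- Section 7.7 gives general stepwise reductions and no order of precedence.
- Section 7.7.1 stops drug at Grade 4 for other events, but its heading limits it to toxicities not related to the liver.
- Section 7.1.1 covers the monitoring schedule and bilirubin above 3× ULN.
- Section 7.8 lets the investigator stop drug for any adverse event. That is discretion and does not rank the rows.
- Section 8.1 lists liver events under "Also considered serious for the purposes of this study", including ALT above 8× "ULN without bilirubin elevation (defined as total bilirubin" is below a stated limit). This governs reporting, not dosing.
- Section 9.2 provides periodic review of toxicities and dose modifications and sets no dosing rule.

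**4. Can the patient be enrolled, and when would the conflict matter?**

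Under "No significant organ dysfunction with initial labs", Section 5.1.i allows bilirubin up to 1.5 mg/dL and AST/ALT up to 1.5× ULN. Exclusion 5.2.g begins "Subjects who have both bilirubin >ULN" and also requires raised AST/ALT, so it does not exclude a Gilbert's patient with normal transaminases.

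In the 14-day run-in, the only scheduled liver test on drug is at the end of week 2 (Section 7.1.1, Appendix A), when essentially no run-in dose is left to hold. Barring unscheduled tests, the conflict can change dosing only in maintenance. Section 7.0, footnote G, reserves maintenance "for those randomized to the treatment who had a response by imaging, to be continued for 1 year", and Section 11.4 makes it optional.

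**5. How often?**

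- From Section 14.2: 21 patients randomized 2:1, so 21 × 2/3 = 14 on pazopanib.
- Assumed, not in the documents: n = 3 to 7 of the 14 enter maintenance. Gilbert's syndrome and AST/ALT above 8× ULN each occur with probability a = 0.05 to 0.10, independently.
- Section 2.4 reports 13 subjects with ALT above 8× ULN, 5 of them above 20×, without a denominator, so no rate can be taken from it.

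The probability per patient is p = a². The expected number is n × p, and the chance of at least one is 1 − (1 − p)ⁿ.

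| n | a | p | Expected patients | Chance of at least one |
|---|---|---|---|---|
| 3 | 0.05 | 0.0025 | 0.0075 | 0.75% |
| 3 | 0.10 | 0.01 | 0.03 | 2.97% |
| 7 | 0.05 | 0.0025 | 0.0175 | 1.74% |
| 7 | 0.10 | 0.01 | 0.07 | 6.79% |

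**The case against.** The strongest reply is that a sensible reading exists. The Gilbert's row directly follows the row that permanently discontinues drug for AST/ALT above 3× ULN with bilirubin above 2× ULN, and it reuses the 3× threshold. It may be meant only to spare Gilbert's patients from that combined rule, leaving the 8× hold in force. This is plausible and may well be the intent. But the table does not say so, and letting the specific row override the general one is an equally ordinary reading with the less safe result.

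It can also be said that the safeguards are adequate: investigators may stop drug, principal investigators review toxicities and dose modifications together, and Section 9.1 names only two centers for record monitoring. These lower the chance of harm or inconsistency. They do not settle what the table instructs. The reporting rule in Section 8.1 offers less protection than it seems to. Its two liver bullets together appear to make ALT above 8× ULN serious, but their bilirubin definitions look garbled, and an AST-only rise, which does trigger the hold row, is not covered.

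Finally, the frequency range rests entirely on assumed inputs, and its upper end is probably too high. The Gilbert's row also needs a mild bilirubin rise at the time, and the arithmetic makes no allowance for that or for the entry limits. This stands: 6.8% is better read as an assumption-driven ceiling than as an estimate.

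**Conclusion.** The concern holds, and it is minor. Above 8× ULN the hold row and the Gilbert's row both apply, their actions conflict, and the protocol gives no order of precedence. That conclusion rests on the table's wording and does not depend on the assumed rates. The size does depend on them: 0.0075 to 0.07 expected patients. There is no effect on the primary analysis. The primary endpoint is the SUV change over the run-in, and on scheduled testing the conflict changes dosing only afterwards, in maintenance.

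**What to change.** Amend one line of the Section 7.7.2 table. Either limit the Gilbert's row to AST/ALT above 3× and up to 8× ULN, or add to the hold row that it applies whether or not the patient has Gilbert's syndrome. Either edit removes the conflict above 8× ULN. Neither defines mild, so the same amendment could usefully state a bilirubin limit for the Gilbert's row, to keep it clear of the discontinuation row that starts above 2× ULN.

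The clinical cost is that a rare patient has drug held temporarily. If the interruption lasts more than 3 weeks, Sections 7.5 and 7.8 end treatment for that patient. The change can wait for the next amendment and leaves sample size, endpoints and analysis untouched.

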7.7.3 Chemotherapy Dose Modifications

A treatment cycle may not begin unless the patient's absolute neutrophil count (ANC) is $\geq 1500/\mu\text{L}$ and platelet count is $\geq 100,000/\mu\text{L}$ (without transfusion).

Patients who experience Grade 3 or 4 hematologic or non-hematologic toxicity that is attributable to chemotherapy and not to the underlying disease should have chemotherapy held until the toxicity resolves to \leq Grade 1. Dose modifications for doxorubicin and ifosfamide-related toxicity will be based on the Investigator's discretion.

Patients who are delayed greater than 3 weeks due to non-resolution of such toxicity will be taken off study.

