7.0 TREATMENT PLAN

TREATMENT	PAZOPANIB RUN-IN ^A	CYCLES 1 AND 2 ^B	CYCLES 3 AND 4 ^C	PRE- OP RT ^D	SURGERY ^E	CYCLES 5 AND 6 ^B	POST-OP RT ^F
DOXORUBICIN		75 MG/M2 CIVI OVER 3 DAYS, EACH CYCLE WEEKS 3-8	75 MG/M2 CIVI OVER 3 DAYS, EACH CYCLE WEEKS 9-14	WEEKS 16-21	2-4 WEEKS AFTER COMPLE- TION OF PRE- OPERATIVE THERAPY	75 MG/M2 CIVI OVER 3 DAYS, EACH CYCLE 2-4 WEEKS AFTER SURGERY	2-4 WEEKS AFTER COMPLETION OF CHEMO-THERAPY
IFOSFAMIDE		2 GM/M2 IV, DAYS 1-5, EACH CYCLE WEEKS 3-8 (6-DAY WASHOUT AFTER PAZOPAN -IB	2 GM/M2 IV, DAYS 1-5, EACH CYCLE WEEKS 9-14			2 GM/M2 IV, DAYS 1-5, EACH CYCLE 2-4 WEEKS AFTER SURGERY	

TREATMENT	PAZOPANIB RUN-IN A	CYCLES 1 AND 2B	CYCLES 3 AND 4C	PRE- OP RT D	SURGERY E	CYCLES AND 6B 5	POST-OP RTF
MESNA^I		AFTER EACH DOSE OF IFOS	AFTER EACH DOSE OF IFOS			AFTER EACH DOSE OF IFOS	
PAZOPANIB OR PLACEBO	800 MG PO DAILY, WEEKS 1-2						
PAZOPANIB MAINTEN- ANCE^G							1 WEEK AFTER COMPLETION OF CHEMO/RT (DURATION 52 WEEKS)

A Pazopanib versus placebo run-in 14 days

B Chemotherapy cycles every 21 days. Cycle 1 may not commence until a 6 day washout period of pazopanib has occurred.

C Cycles 3 and 4 will only be given if there is a response to chemotherapy identified on imaging after cycles 1 and 2.

D Pre-operative radiation administration, when given, will consist of external beam 50 Gy in 25 fractions of 2 Gy/fraction over 5 weeks. If the target volume encompasses sensitive structures such as bowel or lung, the dose can be reduced to 45 Gy in 25 fractions of 1.8 Gy without protocol violation.

E Surgery should be planned for 2-4 weeks after completion of pre-operative therapy. Any planned post surgical adjuvant chemotherapy should be initiated only after adequate wound healing has been achieved. Patients who require a delay of greater than 10 weeks from the initial surgery due to inadequate wound healing will be removed from further protocol therapy.

F Post-operative radiation administration, when given, will consist of external beam 50 Gy in 25 fractions of 2 Gy/fraction over 5 weeks, followed by 10 Gy boost (in 5 fractions) to a reduced, or boost, volume. For contaminated or close margins, the boost dose will be 10 - 16 Gy; for microscopically positive margins, 16 - 20 Gy, and for grossly positive margins, 20 – 26 Gy.

For patients who received pre-operative radiation, but have positive surgical margins, 16 – 20 Gy (2Gy x 8 - 10 fractions) will be given by external beam following any planned adjuvant chemotherapy.

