7.5 Duration of Therapy

Treatment should continue until the end of protocol therapy, defined as the completion of all adjuvant treatments following surgical resection of the primary tumor, or until one of the following criteria applies:

- Disease progression,
- Intercurrent illness that prevents further administration of treatment,
- Unacceptable adverse events(s),
- Greater than 3-week delay in therapy due to adverse event
- The subject or legal representative requests to withdraw from the study, or
- Changes in the subject's condition render the subject unacceptable for further treatment in the judgment of the Investigator.

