7.8 Criteria for Evaluability and Removal/Withdrawal from Treatment

Criteria for evaluability of the Trial

- Patients must have received a total of at least 80% of the intended dose of doxorubicin, ifosfamide, and pazopanib to be evaluable for the trial. If less than this amount is received, the patient may remain on the study, but will not be evaluated for primary endpoints.

Criteria for stopping therapy:

- Substantial non-compliance with the requirements of the study.
- Any adverse event which, in the Investigator's opinion, requires termination of the study medication.
- Disease progression, unless at the discretion of the Investigator (in collaboration with Novartis) continued treatment with study drug is appropriate.
- The patient would benefit from additional radiation therapy beyond that specified in the protocol.
- Request by the patient or a legal representative/relative to stop the treatment.
- The patient presents with a beta-HCG test consistent with pregnancy. Pregnancy will be reported along the same timelines as a serious adverse event.
- The patient uses illicit drugs or other substances that may, in the opinion of the Investigator, have a reasonable chance of contributing to toxicity or otherwise interfering with results.
- The development of a second malignancy that requires treatment, which would interfere with this study.
- The patient is lost to follow-up.
- Interruption in administration of pazopanib or chemotherapy for greater than 3-week delay.
- Development of an intercurrent illness or situation which would, in the judgment of the Investigator, affect assessments of clinical status and study endpoints to a significant degree.

Criteria for study withdrawal:

- Study closure.
- Patient decision to withdraw from both study therapy and follow-up.

The Investigator will make every reasonable effort to keep each patient in the study unless it is in the patient's best interest to discontinue participation. If a patient is removed from the study or declines further participation, all End of Treatment evaluations should be performed if the patient is willing and able to be assessed. A description of the reason(s) for withdrawal from the study will be recorded on the case report form (CRF). The Investigator should also ensure that all patients are followed up for survival and recurrence after the Final Visit.

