Relevant visit data should be entered on the CRF and any unused study medication will be accounted for and returned for all patients participating in the study, even for a brief period of time. Patients who discontinue following entry will have relevant information completed and recorded on the CRF. All patients who discontinue because of adverse events or clinically significant laboratory abnormalities should be followed up until they recover or stabilize, and the subsequent outcome will be recorded. If any patient should die during the trial or within 30 days of stopping study treatment, the Investigator will inform the IRB and the Novartis representative. The cause of death should be recorded in detail, within 24 hours, on a serious adverse event (SAE) form and reported to the IRB and Novartis.

Subjects who are withdrawn from the study prior to surgery will be replaced and randomized to treatment with pazopanib versus placebo according to the 2:1 design.

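### A chemotherapy-toxicity delay of more than 3 weeks takes a patient off study in Section 7.7.3 but only off therapy in 7.5 and 7.8, leaving replacement and primary-analysis status undefined

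*Combined protocol and SAP*

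**What the plan says.** Section 7.7.3 concerns "Grade 3 or 4 hematologic or non-hematologic toxicity that is attributable to chemotherapy and not to the underlying disease". Chemotherapy is held until recovery, and then: "Patients who are delayed greater than 3 weeks due to non-resolution of such toxicity will be taken off study".

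Two other sections address a delay of the same length:
- Section 7.5, among the reasons for treatment to end: "Greater than 3-week delay in therapy due to adverse event".
- Section 7.8, under the criteria for stopping therapy: "Interruption in administration of pazopanib or chemotherapy for greater than 3-week delay".

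Section 7.8 has a separate, shorter list for withdrawal from the study. It has two entries: closure of the study and "Patient decision to withdraw from both study therapy and follow-up".

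The replacement rule, also in 7.8, is tied to study withdrawal: "Subjects who are withdrawn from the study prior to surgery will be replaced and randomized to treatment with pazopanib versus placebo", in the 2:1 design. Section 14.1 expects the primary pharmacodynamic analysis to leave out patients whose data are incomplete because of missed PET scans or study withdrawal for toxicity.

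For the post-operative period, footnote E of the Section 7.0 treatment table says that patients who need a "delay of greater than 10 weeks from the initial surgery due to inadequate wound healing will be removed from further protocol therapy".

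**The concern.** The protocol gives one event two dispositions, and two other rules depend on which applies. A pre-operative patient with a long toxicity delay is replaced if 7.7.3 governs and is not replaced if 7.5 and 7.8 govern. The same choice may decide whether that patient is handled as a toxicity withdrawal in the primary analysis.

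The affected patients are selected by how badly they tolerated treatment, and safety of the pazopanib-chemotherapy sequence is a secondary objective. In a trial of 21 patients, replacement and analysis status should not depend on which section a site reads first.

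The post-operative time limits raise a separate and smaller question: how long may adjuvant chemotherapy wait for wound healing before protocol therapy ends?

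**Working it through.** **1. The two labels.** The event is a delay of more than 3 weeks from unresolved Grade 3 or 4 chemotherapy toxicity, before surgery.

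| Question | If 7.7.3 governs | If 7.5 and 7.8 govern |
|---|---|---|
| Status | Off study | Off therapy, still on study |
| Among 7.8's study-withdrawal reasons? | No | Not applicable |
| Replaced under 7.8? | Yes, if off study means withdrawn | No |
| Toxicity withdrawal under 14.1? | Possibly | No |
| Followed for recurrence and survival? | Yes (7.6, 7.8) | Yes (7.6, 7.8) |

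The difference is more than loose wording, because the protocol separates the two states elsewhere. Table 1 in 7.7.1 repeatedly stops the investigational product while continuing follow-up, and 7.7 removes patients from protocol treatment when the dose would fall below the lowest level.

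**2. Timing against the primary endpoint.** Section 14.1 defines the primary endpoint as percent change in SUV from baseline to the end of the 14-day run-in. Section 4.3 places the second PET before chemotherapy starts. A patient delayed by chemotherapy toxicity therefore normally has the complete pair. Read strictly, 14.1 excludes only incomplete data, so the pair should stay in. The section does not say so for a patient labelled a toxicity withdrawal.

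**3. What replacement does.** The replacement is newly randomized 2:1 and is not matched to the arm that lost a patient. The documents do not say whether the replaced patient's run-in data are kept. If kept, the analysed number exceeds 21. If dropped, patients leave the primary comparison after randomization because of toxicity.

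**4. The dose rule.** Sections 7.8 and 11.0 require 80% of the intended dose of all three drugs for evaluability, and 11.0 counts this over the first 2 cycles. A patient stopped after one full cycle has 1/2 = 50% of the two-cycle chemotherapy dose and is not evaluated for primary endpoints. Ending replacement alone would leave that patient both unreplaced and excluded.

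**5. Scale.** Inputs from 14.2: difference 30 points, SD 20, n = 21 at 2:1 (14 and 7). Two-sided alpha 0.05 is assumed, since none is stated. The normal approximation is

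power = Φ(30 / (20 × √(1/n₁ + 1/n₂)) − 1.96)

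- 14:7 gives Φ(3.24 − 1.96) = 0.900, which reproduces the plan's 90%.
- 13:7 gives 0.892.
- 12:6 gives Φ(3.00 − 1.96) = 0.851.

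By t-test, 14:7 gives 0.867 and 12:6 gives 0.804. By simulation of the planned Wilcoxon test with normal data, they give about 0.84 and 0.75. The numbers lost are assumptions.

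**6. Post-operative limits.** Section 7.0 schedules post-operative chemotherapy 2 to 4 weeks after surgery. Adding 3 weeks puts the 7.5 and 7.8 limit at weeks 5 to 7, if delay is counted from the planned start. Footnote E runs to week 10. The passages disagree over a span of 10 − 7 = 3 to 10 − 5 = 5 weeks. Poor wound healing fits the adverse-event definition in 8.1, and 10.2 lists it as expected with ifosfamide, so 7.5 can apply.

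**The case against.** The strongest reply is that this is a labelling slip with little consequence, and several parts of that reply stand.

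- **Follow-up.** A reader might infer that off study means losing progression, survival or necrosis data. The documents do not support this. Section 7.6 gives a subject who discontinues the study a Final Visit and continued follow-up. Section 7.8 asks for end-of-treatment evaluations even after removal from the study, and for recurrence and survival follow-up of all patients. Section 11.3.3 examines all primary tumor specimens.
- **Footnote E against 7.7.3.** A reader might also infer that footnote E contradicts 7.7.3. Normally it does not, because 7.7.3 is limited to severe toxicity attributed to chemotherapy. Footnote E's consequence, removal from therapy, agrees with 7.5 and 7.8. Only the time limits are in tension. Footnote E can be read as a specific rule overriding a general one, and a course not yet begun is arguably not an interruption under 7.8. No text says so.
- **Footnote E and replacement.** Footnote E applies after surgery and replacement only before it, so footnote E cannot affect who is replaced.
- **Central control.** Registration and randomization are central and there are bi-monthly review meetings, which limits divergence between sites. These arrangements do not supply the missing rule.
- **Size.** No rate of long delays is given. One patient is 1/21 = 4.8% of the trial, but that is true of any patient and is not an effect size.

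The reply leaves the contradiction itself untouched, along with its bearing on replacement and analysis status.

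**Conclusion.** Section 7.7.3 contradicts 7.5 and 7.8 on whether a toxicity delay of more than 3 weeks ends study participation or only therapy, and it uses a ground that 7.8's withdrawal criteria do not recognise. Before surgery, the label decides replacement and may decide primary-analysis status, although the run-in endpoint is normally already measured.

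The size cannot be estimated from the documents. The power figures show only that 21 patients, with no stated dropout allowance, leave little room for avoidable exclusions. A reader might infer that removals would differ by arm. That would require pazopanib to add to chemotherapy toxicity, which the documents do not establish for this sequence.

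The footnote E point is a separate inconsistency of 3 to 5 weeks in a post-operative limit, assuming delay is counted from the planned start of adjuvant chemotherapy. It does not touch the run-in endpoint. Both points merit correction because they are cheap to settle in advance and hard to settle neutrally afterwards.

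**What to change.** 1. In 7.7.3, replace removal from the study with removal from protocol treatment and follow-up under Sections 7.6 and 7.8. This changes the patient's status, not the 3-week limit.
2. In 7.8, state that stopping treatment for toxicity or delay is not study withdrawal for the replacement rule.
3. In 7.8, 11.0 and 14.1, state that a completed run-in PET pair stays in the primary run-in SUV analysis whatever chemotherapy is later received. Without this, the 80% dose rule could exclude a patient whom step 2 leaves unreplaced.
4. Reconcile footnote E with the 3-week limits in 7.5 and 7.8 and say which governs after surgery. That choice belongs to the investigators, and no limit is proposed here.

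The cost is protocol wording. The small downside is fewer replacements, so slightly fewer patients complete all chemotherapy.
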